5.6 Study Time and Events Table

Study Procedure	Screening	CRT	Pre-Surgery	Surgery	Adjuvant Treatment for 12 mos. from 4 to 6 weeks after surgery	Follow-up
Study Interval	Day-1 to -21	Weeks 1-7		Weeks 8-12	Every 2 mos. (28 day cycle)	Every 3 mos. after 12 mos. timepoint
Medical history and Examination	X					X
Screening, Labs, pregnancy	X					
Informed consent	X					
Biopsy	X			X		
Temozolomide Dosing ^a	X					X
RT Planning	X					
Radiation Therapy + Temozolomide		X				
Surgery				X		
Adjuvant Temozolomide					X ^e	
MRI	X		X		X	X
Weight	X	X		X	X	X
CBC/d ^b	X	X	X	X	X	X
QOL Questionnaires (MDASI-BT)	X		X		X	X
Concomitant medication Review	X	X			X	X
Adverse events Review ^d	X	X	X	X	X	X

a Temozolomide will continue in the adjuvant setting for a total of 12 weeks

b CBC/d weekly during neoadjuvant CRT +/- 3 days, and pre-surgery

c From the time of informed consent to the end of the study, 26 months.

d. Adjuvant Temozolomide (C1) schedule no later than 4 to 6 weeks from surgery

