5.5.5 Drug therapy – Temozolomide (Standard of Care)

Refer to the package insert for detailed pharmacologic and safety information of Temozolomide

Dosing

Temozolomide During Concomitant Radiation Therapy

Protocol treatment must preferably begin on the same day as the first fraction of radiotherapy (+/- 48 hours allowed for logistic reasons). Temozolamide will be administered continuously from day 1 of radiotherapy to the last day of radiation at a daily oral dose of 75 mg/m^2 for a maximum of 49 days. The drug will be administered orally daily during radiotherapy, as best tolerated by the patient. During weekends without radiotherapy (Saturday and Sunday), the drug will be taken in the morning. The dose will be determined using actual body surface area (BSA) as calculated in square meters at the beginning of the concomitant treatment. The BSA will be calculated from the height obtained at the pretreatment visit. Capsules of temozolomide are available in 5, 20, 100, 140, 180, and 250 mg. The daily dose will be rounded to the nearest 5 mg.

Post-Radiation – Post Operative Temozolomide

The start of the first cycle will be scheduled as soon as patient recovered from surgery and surgical wound has healed, but no later than 4 to 6 weeks from surgery. After the first post surgery visit to start TMZ (Cycle 1, Month 1), all subsequent cycles (2-12) will be scheduled every 4 weeks (28 days \pm 3 days) after the first daily dose of temozolomide of the preceding cycle.

In all treatment arms, temozolomide will be administered orally once per day for 5 consecutive days (days 1-5) of a 28-day cycle, up to 12 cycles. Patients demonstrating continued benefit from the adjuvant temozolomide can continue treatment to a maximum of 12 cycles. The starting dose for the first cycle will be $150 \text{ mg/m}^2/\text{day}$, with a single dose escalation to $200 \text{ mg/m}^2/\text{day}$ in subsequent cycles if no treatment-related adverse events > grade 1 are noted.

28 days (-3/+5) days after the last day of radiotherapy.

The dose will be determined using the BSA calculated at baseline. The BSA will be re-calculated at the pretreatment visit and if a change in more than 10% in weight has occurred, the dose of temozolomide must be adjusted according to the new BSA. Capsules of temozolomide are available in 5, 20, 100, 140, 180, and 250 mg. The daily dose will be rounded to the nearest 5

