mg. The exact dose administered should be recorded in the CRF. Each daily dose should be given with the least number of capsules.

Prior to each treatment cycle with temozolomide a complete blood count (CBC) will be obtained (within 72 hours prior to dosing). Patients will be suggested to fast at least 2 hours before and 1 hour after temozolomide administration. Water is allowed during the fast period. Patients will be instructed to swallow the capsules whole, in rapid succession, without chewing them. Treatment should be given at night. If vomiting occurs during the course of treatment, no re-dosing of the patient is allowed before the next scheduled dose.

Antiemetic prophylaxis with a 5-HT3 antagonist is strongly recommended and should be administered 30 to 60 minutes before temozolomide administration.

Patients will be treated with post-radiation post-operative temozolomide for 6-12 cycles unless there is evidence of tumor progression or treatment-related toxicity

Pneumocystis carinii prophylaxis is strongly recommended during the radiation phase

Hepatic toxicity including liver failure has been observed in patients enrolled in clinical studies utilizing temozolomide. In addition, liver toxicity may occur several weeks or more after initiation of treatment or after temozolomide discontinuation. For patients with significant liver dysfunction, the risks and benefits of treatment continuation should be carefully considered.

Dose Modifications

Temozolomide During Concomitant Radiation Therapy

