Cases of hepatic injury, including fatal hepatic failure, have been observed in patients enrolled in clinical studies utilizing the agent temozolomide. In addition, it was noted that liver toxicity may occur several weeks or more after initiation of treatment or after temozolomide discontinuation. For patients with significant liver function abnormalities, the risks and benefits of treatment continuation should be carefully considered. Reference TABLE 2 below.

TABLE 2: Temozolomide Dose Levels for Maintenance Treatment

Dose Level	Dose (mg/m ² /day)	Remarks
-1	100	Reduction for prior toxicity
0	150	Dose during Cycle 1
1	200	Dose during Cycles 2-6 in absence of toxicity

Post-Radiation Post-Operative (Adjuvant) Temozolomide

Dosing is based on adverse events (AEs) during the prior treatment cycle. If multiple AEs are seen, the dose administered should be based on the dose reduction required for the most severe grade of any single AE.

On day 1 of each cycle (within the prior 72 hours), ANC $\geq 1.5 \times 10^9/L$, platelet count $\geq 100 \times 10^9/L$ and all treatment-related grade 3 or 4 non-hematologic AEs (except nausea and vomiting unless the patient has failed maximal antiemetic therapy and fatigue) must have resolved (to grade ≤ 1).

If these re-treatment parameters are not met, the treatment will be delayed to a maximum of 4 consecutive weeks. If, after 4 weeks of delay, re-treatment parameters are not met: then any further adjuvant treatment with temozolomide should be stopped.

Dose escalation

If, during the first cycle, all treatment-related non-hematologic AEs observed were grade ≤ 2 (except nausea and vomiting unless the patient has failed maximal antiemetic therapy and fatigue) and with platelets $\geq 100 \times 10^9/L$ and ANC $\geq 1.5 \times 10^9/L$: then the temozolomide dose should be escalated to dose level 1 and this dose should be used as the starting dose for subsequent cycles. If treatment after cycle 1 has to be delayed because of ongoing non-hematologic AEs of grade ≥ 2 , then no escalation is possible. If the dose was not escalated at cycle 2, then the dose should not be escalated in further cycles.

Dose reductions

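### A footnote in the Time and Events Table limits adjuvant temozolomide to 12 weeks, contradicting the same table's 12-month column header and the 6-12 cycles in section 5.5.5

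*Combined protocol and SAP*

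**What the plan says.** **Duration.** Footnote a in section 5.6 reads "Temozolomide will continue in the adjuvant setting for a total of 12 weeks". The adjuvant column of the same table is headed "Adjuvant Treatment for 12 mos. from 4 to 6 weeks after surgery". Section 5.5.5 gives the regimen in cycles: "temozolomide will be administered orally once per day for 5 consecutive days (days 1-5) of a 28-day cycle, up to 12 cycles"; then "Patients demonstrating continued benefit from the adjuvant temozolomide can continue treatment to a maximum of 12 cycles"; and later "Patients will be treated with post-radiation post-operative temozolomide for 6-12 cycles unless there is evidence of tumor progression or treatment-related toxicity". The scheduling text in 5.5.5 numbers the cycles after the first as 2 to 12, and its dose-reduction text covers cycles 3 to 12. Table 2, printed twice in 5.5.5, annotates dose level 1 with "Dose during Cycles 2-6 in absence of toxicity".

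**Start.** Section 5.5.5 ties cycle 1 to recovery from surgery and wound healing, with a latest date of 4 to 6 weeks after surgery. Footnote d in 5.6 repeats that latest date. Section 5.5.5 also contains a line standing alone: "28 days (-3/+5) days after the last day of radiotherapy". The table puts surgery at weeks 8-12.

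**Link to the endpoint.** Section 5.7 counts MRI-defined progression from 3 months after therapy is completed. It does not say whether that means chemoradiation, surgery or adjuvant temozolomide.

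**The concern.** The schedule table is what site staff work from, and two figures in that one table cannot both be followed. A clinician using footnote a would stop adjuvant temozolomide at a point where section 5.5.5 continues it. Either action could be recorded as compliant or as a deviation, depending on the page consulted.

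In a single-arm trial judged against a historical 50% progression rate, the regimen has to be fixed if the result is to be interpretable. The experimental element is the sequence of treatments, so an uncontrolled difference in adjuvant exposure would mix with it. Overall survival, adverse events and later progression-free survival are the outcomes most exposed.

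**Working it through.** **Inputs.** Cycle length 28 days with 5 dosing days, and dose levels of 150 mg/m²/day in cycle 1 and 200 mg/m²/day afterwards without toxicity (5.5.5). Surgery at weeks 8-12 and chemoradiation at weeks 1-7 (5.6). Thirty radiotherapy fractions (5.5.4). Landmark of 7 months (5.9.2).

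**1. Planned duration.** Weeks = cycles × 28 / 7; dosing days = cycles × 5.

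| Source | Stated | Weeks | Cycles | Dosing days | Ratio of weeks to footnote a |
|---|---|---|---|---|---|
| 5.6 footnote a | 12 weeks | 12 | 84/28 = 3 | 15 | 1.0 |
| 5.5.5, lower end | 6 cycles | 24 | 6 | 30 | 2.0 |
| 5.5.5, upper end | 12 cycles | 48 | 12 | 60 | 4.0 |
| 5.6 column header | 12 months | 365.25/7 = 52.2 | 365.25/28 = 13.0 | 65 | 4.3 |

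Footnote a is half of even the lower end in 5.5.5. The other entries are roughly compatible with each other: 12 cycles is 48 weeks, close to 12 months.

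**2. Cumulative dose.** With the stated escalation, the total is 5 × 150 + (cycles − 1) × 5 × 200.
- 3 cycles: 750 + 2 × 1,000 = 2,750 mg/m².
- 6 cycles: 750 + 5 × 1,000 = 5,750 mg/m², ratio 2.1.
- 12 cycles: 750 + 11 × 1,000 = 11,750 mg/m², ratio 4.3.

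Without escalation the totals are 2,250, 4,500 and 9,000 mg/m², with ratios 2.0 and 4.0.

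**3. Difference by the 7-month landmark.** Assume that the 7 months run from the start of chemoradiation, an origin the documents do not fix. Seven months is 7 × 30.4375 / 7 = 30.4 weeks. Reading the column header as a start 4-6 weeks after surgery gives weeks 8 + 4 = 12 to 12 + 6 = 18.
- Start at week 12: cycles begin at weeks 12, 16, 20, 24 and 28, so 5 have begun, against 3 under footnote a. Dose ratio 4,750/2,750 = 1.7.
- Start at week 18: cycles begin at weeks 18, 22, 26 and 30, so 4 have begun, against 3. Dose ratio 3,750/2,750 = 1.4.

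A sixth cycle would begin by the landmark only with a start before week 30.4 − 20 = 10.4.

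**4. The radiotherapy-anchored line.** Thirty fractions on weekdays end at about week 6; the table allows week 7. The line allows 25 to 33 days afterwards: 6 + 25/7 = 9.6 to 7 + 33/7 = 11.7, or about weeks 10-12. That lies inside the surgery window of weeks 8-12, so for a patient operated on late in the window it falls before surgery.

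**5. MRI progression, only if therapy in 5.7 includes adjuvant temozolomide.** With a start at weeks 12-18 and 365.25/84 = 4.35 weeks per month:
- 12 weeks of treatment ends at weeks 24-30 (months 5.5-6.9). Adding 3 months gives months 8.5-9.9.
- 12 cycles ends at weeks 60-66 (months 13.8-15.2). Adding 3 months gives months 16.8-18.2.

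**The case against.** The best reply is that one clerical footnote is out of line with an otherwise coherent plan. The table's footnotes are visibly mis-keyed: marker d sits on the adverse-event row while text d concerns adjuvant temozolomide, marker e has no text, and marker a sits on a general dosing row rather than the adjuvant row. The cycle-based statements agree on a ceiling of 12. This is a fair argument that footnote a may be a slip, but the documents cannot prove it, and it remains a current instruction in the schedule.

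Other parts of the reply limit what may be claimed.
- **Four rival durations.** A reader might count 12 weeks, 12 months, 6-12 cycles and cycles 2-6 as four competing plans. They are not. The Table 2 entry is a remark on a dose level, which leaves cycles 7-12 uncovered but does not end treatment at cycle 6.
- **Fourfold exposure for patients generally.** Fourfold is the largest planned contrast. Treatment stops for progression or toxicity, and section 5.9.1 gives a median progression-free survival of 6.9 months on standard care and anticipates 11-12 months here. Many patients would therefore never reach cycle 12.
- **Two incompatible start rules.** The radiotherapy-anchored line has no subject or verb and never says that adjuvant treatment starts then. The post-surgery wording in 5.5.5 and footnote d sets only a latest date, so after surgery at week 8 a start before week 12 is allowed and the two windows can overlap. Only the column header supports 4 weeks as a minimum.

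**Conclusion.** The point holds in a limited form. Footnote a cannot be met together with the column header above it or with section 5.5.5. For a patient without progression or toxicity, planned duration differs by a factor of 2 (6 cycles) to 4 (12 cycles). By 7 months the difference is about 3 versus 4-5 cycles begun, which rests on the assumed time origin and on a start at weeks 12-18. The Simon design inputs are not involved.

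The Table 2 remark and the orphan radiotherapy line are secondary drafting faults that should be cleared at the same time.

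A reader might infer that the duration conflict shifts the date from which MRI progression counts. The documents support that only if the therapy meant in 5.7 includes adjuvant temozolomide, which they leave open. Even then, with time counted from the start of chemoradiation and a start at weeks 12-18, the earliest countable dates under both durations fall after month 7. Clinical progression counts by a separate route in any case. The missing definition in 5.7 is a separate gap that correcting the footnote would not close.

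The correction is needed because the text governs how long a cytotoxic drug is given.

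**What to change.** The sponsor should:
1. Reconcile footnote a in 5.6 with the column header and with the cycle statements throughout 5.5.5, so that one duration is stated everywhere.
2. Align the Table 2 remark, in both printings, with that duration.
3. Remove the radiotherapy-anchored line in 5.5.5 or reconcile it with the post-surgery start, and make clear whether 4 to 6 weeks after surgery is a window or only a latest date.
4. Re-key the footnote markers in the table.
5. State in 5.7 which therapy's completion starts the 3-month period for MRI progression.

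Which duration and start are intended is a clinical decision for the sponsor and investigators, and none is proposed here. The cost is a protocol wording amendment, with no extra patients or procedures.

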5.7 Primary Endpoints

Phase II Simon Stage 1: No study related undue toxicity or progression in the first stage patients: Toxicity is defined as: progression precluding surgery, unanticipated neurological decompensation, non-completion of neoadjuvant therapy (other than protocol defined dose adjustments or discontinuation), treatment related delay of > 6 weeks to surgery, and/or major unforeseen surgical complication requiring repeat surgical intervention including other than non-life- threatening infection like meningitis/encephalitis or septicemia.

Phase II Stage 2 (Entire Cohort): Progression Free Survival: defined as MRI defined progression (increasing FLAIR, enhancement, diffusion and or perfusion) 3 months after completion of therapy (to allow for excluding pseudo progression) OR clinical progression with new or worsening neurological symptoms related to the tumor (by MRI or clinical correlation with location) and not due to non-tumor or study related symptoms.

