2 ABSTRACT

High grade gliomas, particularly glioblastoma, are the most common malignant primary brain tumors in adults(1). Surgical resection, when feasible, offers the best chance of alleviating the mass effect and increasing the likelihood of durable local control. Whether tumors are resected or deemed unresectable, the standard definitive treatment for high grade glioma is involved field radiation with concurrent and adjuvant temozolomide chemotherapy(2). Additional therapy with anti-VEGF therapies(3, 4) and wearable devices such as alternating electric fields(5) have improved progression free and overall survival modestly.

Unfortunately, most patients recur in the region of the primary tumor, ultimately leading to neurological progression and death in a majority of patients(6). One hypothesis for this progression in the region of the primary tumor has been the persistence of resistant clones, including glioma stem cells(7).

Neoadjuvant, preoperative chemo radiation has consistently shown improvements in local disease control or organ preservation in many cancers including head and neck(8), esophageal(9), rectal(10), bladder cancers(11) and sarcomas(12), leading to improvements in overall survival and limb or organ preservation.

Preoperative therapy has not been well studied in resectable glioblastoma. This study attempts to prospectively assess the feasibility and efficacy of preoperative chemoradiation in improving local control, as this is the predominant mode of failure in these patients leading to poor outcomes.

We plan to do this interventional study in two phases using the Simon two-stage Phase II study design(13). Please see section 5.9 on statistical analysis and plan. In the initial stage if there are no more than 3 unanticipated events after 9 patients, an additional 15 patients will be treated in the second stage of this Phase II study. If no more than 9 of the overall 24 patients overall progress in 8 months the study treatment would be considered significant and worthwhile studying in a future randomized phase III study, comparing preoperative study treatment with standard of care post postoperative chemoradiation to evaluate progression free and overall survival as the end point.

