5.9.2 Statistical Power and Sample Size Considerations

In the Simon two-phase design of this study, if:

p_0 = progression rate of Standard of care = 0.5 (null Hypothesis)

p_1 = Progression after study treatment = 0.25

OR

p_0 = non-progression rate of 0.5

p_1 = non-progression rate of 0.75

With a

Prespecified Type I error rate $\alpha \leq 0.05$

Prespecified Power ≥ 0.8

For non-progression being the response:

The null hypothesis that the true response rate $p_0=50\%$ will be tested against a one-sided alternative. In the first stage $n_1=11$ patients will be accrued. If there are $r_1=6$ or fewer patients responding (i.e. don't progress) in these $n_1=11$ patients, the study will be stopped. Otherwise $n-n_1=14$ additional patients will be accrued to a total of $n=25$. The null hypothesis will be rejected if $r_2+1=17$ or more responses (If >17 of 25 patients do not progress in 7 months) are observed in the ($n=25$) patients. This design yields a type I error rate of 0.05 and a power of 80% when the true response rate (non-progression at 7 months) is $>75\%$.

After completion of 25 patients followed at least for 7 months of the last patient treated, Primary and secondary endpoints will be evaluated and reported.

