7.3 Data Monitoring Plan

The initial Feasibility Phase of the study may be limited to 10 patients. If 3 or more of these patients experience unexpected toxicities, the study will be discontinued. A data monitoring committee formulated specifically for the study would review the project from the Feasibility Phase to Phase II of the project.

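### The stage 1 toxicity list in 5.7 does not name death and its infection clause is ambiguous, so some deaths fall outside the counted events

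*Combined protocol and SAP*

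**What the plan says.** Section 5.7 sets the stage 1 endpoint as absence of undue study-related toxicity or progression, and then defines toxicity by enumeration. The first three items are: "Toxicity is defined as: progression precluding surgery, unanticipated neurological decompensation, non-completion of neoadjuvant therapy (other than protocol defined dose adjustments or discontinuation". The fourth is "treatment related delay of > 6 weeks to surgery". The fifth is "major unforeseen surgical complication requiring repeat surgical intervention including other than non-life- threatening infection like meningitis/encephalitis or septicemia". Death is not named. The progression-free survival definition that follows in 5.7 describes MRI and clinical progression and does not name death either.

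Three other places give a stage 1 rule, and none of them points to this list:

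- Abstract (section 2): "In the initial stage if there are no more than 3 unanticipated events after 9 patients, an additional 15 patients will be treated".
- Section 7.3: "The initial Feasibility Phase of the study may be limited to 10 patients", and "If 3 or more of these patients experience unexpected toxicities, the study will be discontinued".
- Section 5.9.2: a rule on non-progression alone, which stops the trial if 6 or fewer of 11 patients respond.

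Death does appear in section 6.1, as a criterion for a serious adverse event. Under 6.1 an independent safety board receives adverse event data every 3 months. Under 6.3 the IRB is notified of all SAEs. Under 7.3 a study-specific committee reviews the move from the feasibility phase to Phase II.

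**The concern.** The treatments are standard and the sequence is new, so stage 1 exists mainly to find out whether surgery after chemoradiation is safe. A count-based stopping rule works only if each event can be classified in the same way by anyone who applies it. Here the most serious outcome has no item of its own. It counts only when it happens to arrive through another item. The one item on surgical harm depends on repeat surgery, which a patient who dies quickly of a systemic complication may never have. The infection phrase is also unclear on its face, so two assessors could score the same septicemia differently. At stake is the decision whether to expand the trial, taken on about ten patients.

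**Working it through.** **The plan's own figure.** Error rates are stated only for the progression design in 5.9.2 (continue with 7 or more of 11, success with 17 or more of 25, response rates 0.50 and 0.75). Summing P(X1 = x) × P(X2 ≥ 17 − x) over x = 7 to 11, with X1 from 11 patients and X2 from 14, gives a type I error of 0.0458 and power of 0.8005. These agree with the stated 0.05 ceiling and 80%. No error rates are given for the toxicity rules, so there is no plan figure to check on this point.

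**Which deaths meet a listed item?** Section 5.6 places chemoradiation in weeks 1–7 and surgery in weeks 8–12.

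| Death | Item in 5.7 | Counted? |
|---|---|---|
| During chemoradiation | non-completion of neoadjuvant therapy | can be |
| Before surgery, from tumour growth | progression precluding surgery | can be |
| With unanticipated neurological decline | neurological decompensation | can be |
| After completed chemoradiation, before surgery, neither neurological nor from progression | none | no |
| Postoperative, systemic, without re-operation | none | no |
| Postoperative septicemia or meningitis | fifth item | depends on the reading |

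The fourth row is realistic on the protocol's own account. Section 5.5.5 warns of fatal hepatic failure with temozolomide, and of liver toxicity appearing several weeks or more after treatment starts or after it is discontinued. Such a death is not naturally a treatment-related delay to surgery. The third item also has an exemption: "non-completion of neoadjuvant therapy (other than protocol defined dose adjustments or discontinuation". Table 1 in 5.5.5 has temozolomide discontinued for grade 3 or 4 non-hematological toxicity, while the text has radiotherapy proceed. A patient could therefore stop temozolomide under Table 1, finish radiotherapy, die later, and not meet the third item.

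**The infection clause.** Three questions stay open. Does the phrase add infections to the item or remove them? Do the named infections illustrate those that count or those that do not? Must an infection also lead to repeat surgery?

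**Size, as an illustration.** The documents give no toxicity or death rates, so these are assumed: a true event rate of 30%, of which 0, 5 or 10 percentage points are deaths outside the list in patients with no other listed event. The counted rate is then p = 0.30, 0.25 or 0.20. It is also assumed that the 5.7 list governs the stopping rules and that each patient contributes at most one event. The chance of stopping is P(X ≥ k), with X binomial(n, p).

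- Section 7.3, n = 10, k = 3: 1 − [(1−p)^10 + 10p(1−p)^9 + 45p²(1−p)^8]. At p = 0.30 this is 1 − (0.028 + 0.121 + 0.233) ≈ 0.617. At 0.25 it is 0.474, and at 0.20 it is 0.322.
- Abstract, n = 9, k = 4 (continue with no more than 3): 0.270 at p = 0.30, 0.166 at 0.25 and 0.086 at 0.20.

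A single uncounted death reverses the decision when the counted total is one short of the threshold: 2 of 10 under 7.3, or 3 of 9 under the abstract.

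**The case against.** A reader might infer that any fatal complication without re-operation would go uncounted. The documents do not support that. Neurological deaths, deaths during chemoradiation and pre-surgical deaths from tumour growth can each meet a listed item. A fatal septicemia or meningitis counts under one reading of the infection clause, arguably the more natural one.

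A reader might also infer that stage 1 is the trial's only safety gate. It is not: the safety board, the study-specific committee and the IRB would all learn of a death. What stands is that none of these reviews makes the death a counted event. Stage 1 is the only numerical safety rule, not the only safeguard.

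The strongest objection concerns the arithmetic. The rules in the abstract and 7.3 count unanticipated events and unexpected toxicities. Neither term is defined by reference to 5.7, so an unexpected death could be counted there by judgement. The rates are assumed, and 10 points of uncounted death out of 30 would mean that one third of patients with an event die in a narrow residual category. Both criticisms are fair. The figures show how sensitive so small a rule is to a missing category, and they do not estimate the loss in this trial. The missing link is itself a defect, because whether a death counts is then settled only after it has happened.

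**Conclusion.** The point holds in a limited form. Followed literally, the 5.7 list leaves out at least two kinds of death: non-neurological, non-progression deaths between completed chemoradiation and surgery, and postoperative systemic deaths without re-operation. It also leaves the status of serious infections undecided. The progression-free survival definition does not expressly close the gap.

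Under the assumed 30% event rate, and if 5.7 governs the stopping rules, 5 to 10 points of uncounted deaths lower the chance of stopping from 0.62 to 0.47–0.32 under 7.3. Under the abstract's rule, 10 points lower it from 0.27 to 0.09. That deaths are missing from the list follows from the text alone. The size rests on assumptions that the documents neither support nor exclude. The change should be made before stage 1 is assessed.

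**What to change.** 1. In 5.7, add death as a stage 1 event over a stated window. The window needs a fixed end that also applies to patients who never have surgery or never start adjuvant temozolomide; otherwise it would not close for them. The investigators should decide, and write down beforehand, whether deaths clearly unrelated to study treatment are excluded.
2. Restate the infection clause as a positive list of the infections that count, and say whether re-operation is also required. The content is for the investigators to decide.
3. Make the stage 1 rules in the abstract and 7.3 refer to this one definition, and say whether they count events or patients. Reconcile them with each other and with 5.9.2, since the three now give 9, 10 and 11 patients and different triggers.

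The cost is a few sentences and no new data collection, because deaths are already recorded as SAEs. The downside is a slightly higher chance of stopping if an unrelated death occurs, which the choice in item 1 can limit.

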5.9.1 Statistical Analysis Plan

The Simon two-stage design will be used.

The median progression-free survival of these patients with current standard of care therapy is in the range of 6-8 months (6.9 months in the standard of care). With the proposed trial of surgical resection of the tumor after chemotherapy and radiation the median progression free survival is anticipated to be approximately 11-12 months from subset analysis of available literature and based on prior data on other disease sites. In other words, the 7-month local progression rates is anticipated to decrease from 50% to 25%, or progression free survival improve from 50-75% Due to assessment of unanticipated adverse events with this novel sequencing of established treatment, a Simon two-stage phase II study design would be used to proceed with the study treatment after meeting prespecified events in the initial phase, with goal being to determine whether the new treatment paradigm is sufficiently promising to warrant a major controlled clinical evaluation against the standard therapy

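### The written 7-month primary endpoint and responder rule leave out death, and neither the completion of therapy nor the start of the 7 months is defined

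*Combined protocol and SAP*

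**What the plan says.** **Endpoint (5.7).** The label is Progression Free Survival. The definition has two limbs. The MRI limb is "defined as MRI defined progression (increasing FLAIR, enhancement, diffusion and or perfusion) 3 months after completion of therapy (to allow for excluding pseudo progression"). The clinical limb is new or worsening neurological symptoms "related to the tumor (by MRI or clinical correlation with location) and not due to non-tumor or study related symptoms". Neither limb mentions death.

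**Benchmark (5.9.1).** Median PFS under standard care is given as 6.9 months. The target is that "the 7-month local progression rates is anticipated to decrease from 50% to 25%, or progression free survival improve from 50-75"%.

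**Decision rule (5.9.2).** Response is non-progression, with null 0.50 and alternative 0.75. Of the first 11 patients, 6 or fewer responders stops the trial. Otherwise 14 more are accrued, and the null is rejected at 17 "or more responses (If >17 of 25 patients do not progress in 7 months"). The stated type I error is 0.05 and the power 80% "when the true response rate (non-progression at 7 months) is" above 75%.

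**Abstract (section 2).** This also counts progression only, with another sample size and time point: "If no more than 9 of the overall 24 patients overall progress in 8 months the study treatment would be considered significant".

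**Timing.** Section 5.5.5 allows up to 12 adjuvant temozolomide cycles in one place and says 6-12 in another. In the 5.6 table the column heading reads "Adjuvant Treatment for 12 mos. from 4 to 6 weeks after surgery", while footnote a reads "Temozolomide will continue in the adjuvant setting for a total of 12 weeks". Section 5.4.2 measures the 26-month follow-up from registration. No section says where the 7 months begin.

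**The concern.** Setting PFS equal to one minus the progression rate, as 5.9.1 and 5.9.2 do, is valid only if nobody dies without progression. The trial tests surgery after chemoradiation, and section 7.2 accepts that this sequence may carry unforeseen risks. The clinical limb sets aside study-related symptoms, so a fatal complication of the sequence meets neither limb and would add to the success count. If the 50% null includes deaths, as a median PFS normally does, the comparison favours the new sequence.

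The stage 1 toxicity criteria and the DSMB reports watch for such harm but do not score it in the 25-patient test. The stage 1 criteria also apply only to first-stage patients, and 14 of the 25 enter later.

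The two timing gaps are lesser. Their consequence is that two assessors could classify the same patient differently at month 7.

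**Working it through.** **Inputs from 5.9.2.** n1 = 11, continue with 7 or more responders, n = 25, reject at 17 or more; p0 = 0.50, p1 = 0.75, one-sided.

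**Formula.** P(reject) = Σ over x = 7 to 11 of P[Bin(11, p) = x] × P[Bin(14, p) ≥ 17 − x].

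**The plan's own figure.** At p = 0.50 the five terms are:

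| x | P[Bin(11) = x] | needed of 14 | tail probability | product |
|---|---|---|---|---|
| 7 | 0.16113 | 10 | 0.08978 | 0.01447 |
| 8 | 0.08057 | 9 | 0.21198 | 0.01708 |
| 9 | 0.02686 | 8 | 0.39526 | 0.01061 |
| 10 | 0.00537 | 7 | 0.60474 | 0.00325 |
| 11 | 0.00049 | 6 | 0.78802 | 0.00038 |

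The sum is 0.0458. At p = 0.75 the same formula gives 0.8005, so the stated design reproduces with a cut-off of 17 or more. Read literally, the parenthesis (more than 17) means 18 or more, which gives 0.0200 and 0.7011; the stated 80% power is then missed.

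**Uncounted deaths.** Let true 7-month PFS be 0.50 and let a share d die by month 7 without recorded progression. If they score as responders, the apparent response rate is 0.50 + d. The documents give no value for d, so these are assumed values (reject at 17 or more):

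| d | type I error, all 25 patients affected | type I error, only the 14 second-stage patients affected |
|---|---|---|
| 0 | 0.0458 | 0.0458 |
| 2% | 0.0679 | 0.0558 |
| 4% | 0.0975 | 0.0671 |
| 10% (extreme) | 0.2397 | 0.1078 |

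The third column holds the stage 1 rate at 0.50. Type I error reaches 0.05 at an apparent rate of 0.5043 (d = 0.43%, about 1 in 230) if both stages are affected, or at a second-stage rate of 0.5087 (d = 0.87%).

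**When the MRI window opens.** Months from chemoradiation start = weeks / 4.348, plus 3. Chemoradiation is taken to end in week 6-7, surgery to fall in weeks 8-12 (5.6), and temozolomide to start 4-6 weeks later, in weeks 12-18.

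| Reading of completion of therapy | Ends (week) | Window opens (month) |
|---|---|---|
| Chemoradiation | 6-7 | 4.4-4.6 |
| Surgery | 8-12 | 4.8-5.8 |
| Temozolomide stopped after cycle 1, day 5 | 12.7-18.7 | 5.9-7.3 |
| 12 weeks of temozolomide | 24-30 | 8.5-9.9 |
| 6 cycles | 36-42 | 11.3-12.7 |
| 12 cycles | 60-66 | 16.8-18.2 |

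If completed adjuvant treatment is meant, no MRI progression could count by month 7.

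**Which scan decides.** Section 5.5.2 schedules MRI every 2 months after surgery. With the chemoradiation anchor, the first scan at or after window opening can be almost 2 months later: 7/4.348 + 3 + 2 = 6.6 months. With the surgery anchor it is the 4-month post-operative scan, at latest 12/4.348 + 4 = 6.8 months. If the clock starts at registration, up to 21 days earlier (the 5.6 screening interval; 3/4.348 = 0.69 months), these become 7.30 and 7.45 months. The deciding scan can therefore fall after month 7.

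**The case against.** - **The label implies death.** PFS conventionally includes death, the plan uses the term throughout, and 5.4.1 ends participation at progression or death. It is fair to say that death was omitted and not deliberately excluded. But 5.4.1 describes participation and not endpoint events, the label is followed by an explicit definition, and the operative rule in 5.9.2 counts non-progression.
- **The null may be a progression-only rate.** Section 5.9.1 also speaks of local progression. If 0.50 and 0.75 exclude deaths, there is no inflation, and counting deaths would lower power to 0.734 at 2% deaths (p = 0.73) or 0.620 at 5% (p = 0.70). This stands as a condition. However, 5.9.1 ties the null to median PFS and states the target as PFS of 75%.
- **The inflation is assumed and depends on the cut-off.** Both points are true. The low threshold of 0.43% mainly reflects how little room lies between 0.0458 and 0.05. With 18 or more, type I error is 0.0317 at 2% and 0.0485 at 4%, both under 0.05, but that cut-off does not deliver the stated power.
- **The adjuvant reading of the window is unlikely.** Agreed. Excluding pseudoprogression, stopping temozolomide at progression (5.5.5) and MRIs during adjuvant treatment (5.6) all point away from it. Counting to the last dose instead of the full cycle also moves the 12-week opening from 8.5 to 7.8 months ((20 + 5/7)/4.348 + 3), still after month 7. The text does not exclude this reading.
- **Deaths remain visible** in overall survival, SAE reports and three-monthly DSMB reports. They do, but none of these enters the primary test.

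**Conclusion.** The concern holds and must be fixed. As written, the rule that decides the trial can score a death without progression, including a treatment-related one, as a success. The design itself is sound at 17 or more responders (type I error 0.0458, power 0.8005), but those error rates apply only if each patient's 7-month status is defined, deaths included. The inflation to 0.068 or 0.098 is illustrative: it assumes 2% or 4% uncounted deaths, a null that is a true PFS rate, and the 17-or-more cut-off. The finding that death is missing from the rule needs none of these assumptions. The undefined completion of therapy and time origin are confirmed as lesser clarifications.

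**What to change.** **In 5.7:**
- Count death from any cause as a PFS event.
- State the origin of the 7 months, for example registration, in line with 5.4.2.
- Tie the 3-month pseudoprogression window to one named date early enough for 7-month status to be read, for example the last day of chemoradiation.
- Name the MRI that decides 7-month status, with an allowed date range.
- Say how MRI change seen before the window opens is classified at month 7. The confirmation and dating rule is for the investigators to choose.

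**In 5.9.2:**
- Score as a non-responder any patient who is dead or progressed by 7 months, or not documented progression-free at 7 months.
- Use 17 or more in both places.
- Confirm that 0.50 and 0.75 are PFS rates that include death.

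**Elsewhere:** bring the abstract's 24 patients and 8 months into line with 5.9.2. The adjuvant durations in 5.5.5 and 5.6 (up to 12 cycles, 6-12 cycles, 12 months, 12 weeks) must be reconciled.

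**Cost:** a wording amendment that uses deaths already recorded and MRIs already scheduled, though one scan may need a date range. The observed success rate may be slightly lower. Sample size and power stay as stated if 0.50 and 0.75 are PFS rates; if 0.75 is a progression-only rate, power falls as shown above and the design should be rechecked.
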